7.1 Efficacy Evaluation

HAMA score, HAMD response rate, HAMD remission rate, BDI score, GAD-7 score, PCL-C score, SF-36 score, heart rate variability parameters, echocardiography parameters, venous blood biomarkers, and incidence of MACE.

7.2 Safety Evaluation

7.2.1 Baseline Signs and Symptoms

Heart rate, respiratory rate, blood pressure, body temperature, chest tightness, chest pain, shortness of breath, wheezing, dyspnea.

7.2.2 Auxiliary Examination Safety Assessment

Myocardial injury markers, NT-proBNP, coagulation panel, complete blood count, echocardiography.

7.2.3 Physical Examination and Vital Signs

Consciousness, neurological reflexes, breath sounds, heart sounds, skin and mucous membrane condition.

8. Adverse Event Reporting

8.1 Definition of Adverse Events

8.1.1 Definitions

- Adverse Event (AE): Any untoward medical occurrence in a subject administered an investigational treatment, which may manifest as signs, symptoms, disease, or laboratory abnormalities, but does not necessarily have a causal relationship with the treatment.

- Serious Adverse Event (SAE): Any AE occurring in a subject that results in death, is life-threatening, requires inpatient hospitalization or prolongation of existing hospitalization, results in persistent or significant disability/incapacity, is a congenital anomaly/birth defect, or other medically important events.

8.1.2 Severity

- Mild: Tolerable by the subject, does not affect prognosis, does not require special treatment, no impact on recovery.

- Moderate: Causes discomfort to the subject, requires special treatment, has a direct impact on recovery.

- Severe: Life-threatening, causing death or disability, requires immediate emergency treatment.

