6.1 Study Intervention Implementation Steps

1. For outpatients or inpatients who are 2 weeks to 12 months post-ACS PCI, a psychiatrist will conduct assessments using DSM-V, HAMD, and HAMA scales. Patients meeting criteria for mild to moderate depression will be advised to receive appropriate treatment. If they refuse and meet inclusion/exclusion criteria, they will sign informed consent, enroll in the clinical trial, and baseline data will be collected.

2. Device Usage Method

Eligible patients will receive transcutaneous auricular non-invasive vagus nerve stimulation while awake. The electrode and the patient's left ear target area will first be disinfected with 75% alcohol. An abrasive gel will then be applied to the left concha cymba and tragus area for gentle abrasion, wiped off, and the area disinfected again with alcohol. Conductive gel will be applied to the electrode output points. The electrode will be placed on the patient's left ear, ensuring the output points are positioned on the left tragus. Pulses will be delivered via the Xidian Keyue brand (Product No.: BS-TVNS600) vagus nerve stimulator. The stimulation current will be gradually increased to the maximum intensity tolerable by the patient, defined as the threshold intensity.

Active Stimulation Group: Stimulation at threshold intensity, with parameters: pulse frequency 20 Hz, pulse width 250 μ s, pulse current 0.5-3 mA. Stimulation cycle: 30 seconds ON, 30 seconds OFF.

Sham Stimulation Group: Device, parameter adjustment, and placement identical to the active group. The stimulator is programmed to deliver stimulation only for the first 5 seconds of each session, with no subsequent stimulation.

Both groups will undergo electrical stimulation twice daily for 20 minutes each session, for a total treatment duration of 8 weeks.

All patients will be trained on how to turn the stimulator on/off, attach the electrode to the ear and position it, and increase the intensity. All subsequent operations will be performed by the patient at home. Patients can obtain assistance via telephone

or site visits if they have questions. Each patient will be given a diary card to record usage date, duration, adverse reactions, and suggestions. Patients are required to complete daily entries, which will be checked during assessment visits.

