9.6 Data Monitoring Committee

Given the low incidence and mild nature of adverse reactions associated with this trial, and its high safety profile, a Data Monitoring Committee will not be established.

10. Data Collection and Management

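### The severity grades in 8.1.2 largely repeat the SAE criteria, so intense but non-dangerous stimulation discomfort can never be graded severe and has no single grade below that

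*Protocol*

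**What the plan says.** Protocol 8.1.2 has three grades. The top one reads "Severe: Life-threatening, causing death or disability, requires immediate emergency treatment". The middle one, which is the only grade to name discomfort, reads "Moderate: Causes discomfort to the subject, requires special treatment, has a direct impact on recovery". The lowest, which is the only grade to name tolerability, reads "Mild: Tolerable by the subject, does not affect prognosis, does not require special treatment, no impact on recovery".

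No conjunction links the criteria within a grade, apart from the one joining death and disability in the severe grade. The protocol does not say whether they are cumulative or alternative.

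Protocol 8.1.1 defines an SAE as an event that, among other criteria, "results in death, is life-threatening, requires inpatient hospitalization or prolongation of existing hospitalization, results in persistent or significant disability/incapacity".

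Protocol 6.1 sets the intensity as follows: "The stimulation current will be gradually increased to the maximum intensity tolerable by the patient, defined as the threshold intensity". For the arm that receives real treatment, the same section then specifies "Active Stimulation Group: Stimulation at threshold intensity". Patients are trained to operate the stimulator, including raising the intensity, and carry out all later sessions themselves at home, twice daily for 8 weeks. The sham device gives current only in the first 5 seconds of a session.

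**The concern.** Severity describes how intense an event is. Seriousness describes its outcome or the danger it poses. They are normally kept apart because a very painful event can be harmless and a mild one can lead to admission. Section 8.1.2 builds its top grade from seriousness criteria, which leaves no grade for an intense event that is not dangerous.

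For this device that is a foreseeable kind of reaction. The active arm is treated at the tolerance limit, so local discomfort is the likely reason for a patient to turn the device down or off. At stake is the description of tolerability. If the worst non-dangerous reactions can only be mild, moderate or ungraded, a summary by grade would tend to favour the device because of the scale. Two assessors could also grade the same event differently, and both would be following the protocol.

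**Working it through.** No figure is involved, so the check sets the definitions side by side.

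**Step 1: overlap of severe with serious.** Severe in 8.1.2 contains four elements: threat to life, death, disability and need for immediate emergency treatment. The first three are also SAE criteria in 8.1.1. Only the fourth is new, and it too concerns urgency rather than intensity.

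**Step 2: the test event.** Take discomfort that the patient cannot tolerate, that ends when the device is switched off, needs no special treatment, and leaves prognosis and recovery unaffected.

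- Mild: fails on tolerability; meets the other three criteria.
- Moderate: meets discomfort; fails on special treatment and on impact on recovery.
- Severe: meets no criterion.

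**Step 3: grade under each reading.**

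| Mild criteria | Moderate criteria | Resulting grade |
|---|---|---|
| all required | all required | none |
| any suffices | any suffices | mild and moderate |
| all required | any suffices | moderate |
| any suffices | all required | mild |

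Severe is not reached in any row, since the event meets none of its criteria. The first two rows apply one rule throughout; the last two mix rules. One event thus has four possible results.

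**Step 4: limits of the gap.** The no-grade result needs the all-required reading and an event without special treatment or impact on recovery. If the discomfort does need special treatment and does affect recovery, it is moderate on that reading. It is still not severe unless it meets one of the severe criteria.

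**Step 5: hospitalization.** An admission that is not life-threatening or disabling and needs no emergency treatment is an SAE under 8.1.1. It meets no severe criterion in 8.1.2 and so cannot be severe on either reading. If emergency treatment is needed, the event is severe when any criterion suffices and not severe when all are required.

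**Step 6: which arm is exposed.** In the active arm a session of 20 minutes with 30 seconds on and 30 seconds off gives 20 × 30/60 = 10 minutes, or 600 seconds, of current. Sham gives 5 seconds. Discomfort from stimulation would therefore be expected mainly in the active arm, which is where the scale is weakest.

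**The case against.** Several parts of the other side's case stand.

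- The moderate grade names discomfort, so ear discomfort has an obvious place if one criterion is enough. A sensible assessor might require all the mild criteria and any one of the moderate criteria, which gives moderate alone. The protocol does not state that rule, however. Under it, tolerable discomfort that needs no treatment meets both grades, so the overlap moves to another event.
- Current set at the tolerated maximum is tolerable when set. Intolerable discomfort must arise later. Home operation over 8 weeks, by patients trained to raise the intensity, makes that realistic, but no rate is given.
- Section 8.2 asks for manifestations, management, duration, outcome and relationship for each event, and the diary in 6.1 records adverse reactions daily. The raw information is partly kept.

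A reader might also infer four stronger claims that the protocol does not support:

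- *Intolerable discomfort is left without a grade and will also be reported as mild or moderate.* These results need different readings of the same text and cannot both be asserted.
- *Misreporting is certain.* The protocol names no analysis by grade, and 8.2 does not list severity among the recorded items. Only a risk can be claimed.
- *Every hospitalized SAE that is neither life-threatening nor disabling is capped at moderate.* This ignores the emergency-treatment criterion (step 5).
- *The scale props up the decision to have no Data Monitoring Committee.* Section 9.6 reasons in advance: "Given the low incidence and mild nature of adverse reactions associated with this trial". Grades assigned later play no part in that decision.

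**Conclusion.** The point holds in a limited form. The scale in 8.1.2 defines severity largely by seriousness and does not say how its criteria combine. Intense, non-dangerous stimulation discomfort can never be severe. Below severe, it is ungraded if all criteria are required and fits two grades if any one suffices. A hospitalized SAE that is not life-threatening or disabling and needs no emergency treatment also cannot be severe.

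The conclusion that severe is out of reach depends on no choice of reading. The conclusion about inconsistent grades rests on the protocol's silence about how the criteria combine. That tolerability may look better than it is rests on two assumptions: that such discomfort occurs in home use, and that results are summarized by grade. The number of events affected cannot be estimated, because no event rate is given.

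This is a minor safety-reporting flaw. It does not touch the primary endpoint, the sample size, the 24-hour SAE reporting (which turns on seriousness, not grade) or the basis for the committee waiver.

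**What to change.** Replace 8.1.2 with grades of intensity that cover every event and do not overlap, assigning the highest grade that applies:

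- *Mild*: no interference with usual activity.
- *Moderate*: some interference with usual activity.
- *Severe*: prevents usual activity or cannot be tolerated, whether or not it is life-threatening.

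Leave death, threat to life, disability and hospitalization to the SAE definition in 8.1.1.

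Add one field to the adverse-event form recording whether stimulation was reduced, interrupted or stopped because of the event, and report it by arm. This also separates tolerability from compliance. Section 6.3 counts stopping the device on one's own initiative as poor adherence, and 9.2.2 may exclude poor adherers from the per-protocol set, so a patient who stops because of pain could otherwise appear only as non-adherent.

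The cost is the wording of one section and one form field. The downside is that the reported share of severe events may be less favourable.

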8.2 Recording and Reporting Pathway for Adverse Events

Any clinical AEs occurring during treatment will be recorded in detail in the source documents, including time of onset, clinical manifestations, management, duration, outcome, and relationship to the trial. For abnormal laboratory findings, follow-up will continue until results return to normal, baseline levels, or are determined unrelated to the investigational treatment. SAEs will be documented on an SAE form and reported to the clinical research center within 24 hours.

8.3 Risk Prevention and Management

The clinical trial application will be submitted according to regulatory requirements, and the trial will commence only after obtaining approval. Scientific rigor in trial design and strict adherence to inclusion/exclusion criteria will minimize risks. Patient guidance will be strengthened to reduce risks from improper operation. Reasonable safety indicators will be established to lower risk occurrence. Each center will designate a researcher familiar with taVNS procedures as a quality control supervisor responsible for managing risks during treatment.

9. Statistical Analysis

9.1 Sample Size Determination

This is a randomized controlled trial. Significance level (α) is set at 0.05, and power ($1-\beta$) at 0.80. Based on literature, the effect size for taVNS alleviating depression is approximately 57%. Using PASS software, the calculated sample size per group is $n_1=n_2=56$. Considering a 10% dropout/loss-to-follow-up rate and the need for stratification by age and gender, the minimum sample size per group is determined to be 60, resulting in a total sample size of 120.

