2.2 Study Endpoints (or Evaluation Metrics)

2.2.1 Primary Endpoint (or Primary Evaluation Metric) and Definition

Hamilton Depression Rating Scale (HAMD) score at Week 8: The 17-item HAMD is convenient, has clear criteria, is easy to master, and can be used to assess depressive symptoms in various conditions including depression, bipolar disorder, and neurosis, being particularly suitable for major depressive disorder.

Scoring criteria:

No depressive symptoms: Total score ≤ 7 ; Mild depression: Total score ≥ 8 and ≤ 17 ; Moderate depression: Total score > 17 and ≤ 24 ; Severe depression: Total score > 24 .

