5.1 Randomization

5.1.1 Method for Generating Random Allocation Sequence

Stratified block randomization will be used: Eligible patients will be randomly assigned to Group A or B in a 1:1 ratio. Using R software, stratification will be based on age (two levels: 18-60 years, >60 years) and gender (two levels: male, female), resulting in 4 strata. Within each stratum, patients will undergo randomization with varying block sizes. The output will determine the stimulation device assigned to each patient.

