9.3 Efficacy Analysis and Statistical Methods

9.3.1 Analysis of Primary Endpoint

Comparison of HAMD scores between groups will be performed using t-tests or non-parametric tests.

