9.4 Safety Analysis and Statistical Methods

Statistical analysis will be performed using SPSS 26.0 software. Categorical data will be presented as counts and percentages. Normally distributed continuous data will be presented as mean \pm standard deviation; non-normally distributed continuous data will be presented as median and interquartile range. Differences between groups for normally distributed continuous data and categorical data will be compared using independent samples t-tests and chi-square tests, respectively. Non-parametric tests will be used for non-normally distributed continuous data. Bayesian analysis will be employed to further explore the impact of different stimulation modalities on outcome prognosis. All statistical tests will be two-sided, with a P-value <0.05 considered statistically significant.

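### Section 9.1 does not add up as written: 56 per group plus 10% dropout gives 63, not 60, and the 57% effect behind the 56 has no scale that ties it to the Week-8 HAMD score

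*Protocol*

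**What the plan says.** Protocol section 9.1 takes these steps in order:

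- "Significance level (α) is set at 0.05", with power 0.80. Sidedness is not given there, but section 9.4 says "All statistical tests will be two-sided, with a P-value <0.05 considered statistically significant".
- The only effect input, attributed to the literature, is that "the effect size for taVNS alleviating depression is approximately 57" per cent.
- PASS is reported to give 56 per group.
- After that figure, the text brings in a 10% dropout rate and stratification by age and gender, and concludes that "the minimum sample size per group is determined to be 60, resulting in a total sample size of 120".

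The primary endpoint in section 2.2.1 is the "Hamilton Depression Rating Scale (HAMD) score at Week 8", a continuous score. Section 9.3.1 gives its analysis: "Comparison of HAMD scores between groups will be performed using t-tests or non-parametric tests". HAMD response (a reduction of at least 50%) and remission are listed as secondary endpoints in section 2.2.2. Section 5.1.1 has patients "randomly assigned to Group A or B in a 1:1 ratio".

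**The concern.** Two things in this paragraph do not fit.

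First, the dropout step. A reader who follows the text takes 56 as the number needed with data and 60 as the number to randomize so that 56 remain after 10% loss. Sixty does not achieve that. Stratification is offered as a further reason to enlarge, yet the increase does not cover dropout alone.

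Second, the effect input. A comparison of mean scores is sized from a mean difference and an SD, or from their ratio. A percentage is neither. It could be a standardized difference written as a percentage, a response rate, or something else, and each reading gives the 56 a different meaning.

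This paragraph is the only justification for randomizing 120 patients. As it stands, the stated 80% power cannot be linked to any HAMD difference, so a null result could not be read against a known detectable effect.

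**Working it through.** **Inputs from the protocol.** Alpha 0.05, power 0.80, the 57% effect, 56 and 60 per group, and 10% dropout (section 9.1); two-sided testing (9.4); 1:1 allocation (5.1.1); t-test or non-parametric test on the score (9.3.1). *Assumption:* a patient lost before Week 8 contributes no primary score.

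**Step 1: the dropout step, with no assumption about the effect.**

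- Number to randomize = n/(1 − dropout) = 56/0.90 = 62.2, so 63 per group, 126 in total.
- The cruder n × (1 + dropout) = 56 × 1.10 = 61.6, so 62. It also exceeds 60.
- Evaluable from 60 per group = 60 × 0.90 = 54, which is 2 below 56.
- Loss that 60 can absorb while keeping 56 = (60 − 56)/60 = 6.7%.
- Shortfall against the stated rule = 63 − 60 = 3 per group, 6 in total.

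The 60 is therefore not reproduced from the 56.

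**Step 2: can the 56 be reproduced from the 57%?** The scale is not stated, so each reading below is an assumption.

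*Reading A: standardized difference d = 0.57.* Normal approximation: n = 2(1.960 + 0.842)²/0.57² = 48.3, so 49 per group. The exact two-sample t-test (noncentral t) gives power 79.8% at 49 and 80.6% at 50, so 50 per group are needed. This is not 56. However, 50/0.9 = 55.6, which rounds up to exactly 56, so 56 may already include the dropout allowance.

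| Per group | t-test power at d = 0.57 |
|---|---|
| 50 | 80.6% |
| 54 | 83.5% |
| 56 | 84.8% |
| 60 | 87.2% |

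For a rank test at the usual efficiency of 0.955 under normality, 50/0.955 = 52.4, so 53 per group, still within 54.

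*Reading B: 56 is the evaluable requirement at 80% power.* Solving the t-test for 80% power at 56 per group gives d of about 0.534. At that difference, 54 per group give 78.5%, which is 1.5 points under target.

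*Reading C: 57% is the response rate on active stimulation.* The two-proportion formula (pooled variance under the null) needs a sham rate, which the protocol does not give:

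| Assumed sham rate | n per group before rounding up |
|---|---|
| 30% | 51.7 |
| 31% | 56.0 |
| 32% | 60.8 |

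So 56 is reachable with a sham rate near 31%, but the number would then size HAMD response, a secondary endpoint, and leave the Week-8 score without a stated power.

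**Step 3: what 60 per group delivers with 10% loss.** Under A, 54 evaluable exceed the 50 needed and power is 83.5%. Under B, 54 fall short of 56 and power is 78.5%. Under C, power for the primary score is unknown. A and B are alternatives and cannot both apply.

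**The case against.** The strongest defence is that the trial may be sized adequately and only described badly. On reading A every number falls into place: 50 for the t-test, 56 after 10% dropout, and 60 after rounding up for four strata. On reading B the cost is 1.5 points of power. Nothing in enrolment, conduct or analysis would change.

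Much of this stands, and it limits the finding to a reporting correction. It does not remove it. The text presents 56 as the software result and introduces dropout afterwards, so a reader cannot tell that reading A was meant, and neither A nor C can be confirmed from what is written.

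Two stronger readings are tempting and should not be drawn:

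- **That 50 per group is the correct figure and 56 is wrong.** This treats 57% as d = 0.57. The protocol does not say so, and another reading reaches 56. The 56 is unverifiable, not shown to be false.
- **That the effect-size problem and the dropout shortfall add up.** If 50 are needed, 60 per group does cover 10% loss. The shortfall exists only if 56 is the evaluable requirement.

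It might also be said that such detail belongs in a statistical analysis plan, which is not at hand. But the protocol carries out the calculation itself and fixes 120 from it, so the inputs need to be coherent there.

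**Conclusion.** The point holds as a moderate reporting correction. Two statements are firm. As ordered in section 9.1, 60 per group does not follow from 56 with 10% dropout: 63 would be needed, 54 remain, and 6.7% loss is covered. The 57% has no scale, SD or control value, so the 56 cannot be tied to the primary endpoint.

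The effect on power is small wherever it can be computed: 83.5% with 54 evaluable if d = 0.57, and 78.5% if 56 was the evaluable requirement at 80%. Both figures assume a two-sided t-test at 0.05, equal groups and exactly 10% without a Week-8 score. If 57% was a response rate, power for the primary score cannot be stated from the document. The finding does not show that the trial is too small.

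**What to change.** Keep 120 patients and rewrite the paragraph in section 9.1 to:

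1. State the effect as a difference in mean Week-8 HAMD score with its SD, for the test planned in section 9.3.1, and state there that the test is two-sided. If 57% was a response rate, say so, give the sham rate, and recompute for the score.
2. Say whether 56 is before or after the dropout allowance.
3. Make the last step consistent by one of two routes. Either report the power with 54 evaluable per group (83.5% at d = 0.57; 78.5% at d = 0.534), or keep 56 as the evaluable number and give the dropout allowance as 6.7%.
4. If stratification is kept as a reason for the increase, say how many patients it accounts for.

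The cost is one paragraph and a slight change in the stated power or dropout allowance. No extra patients are required.
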